The Phase 1 ACC study provides tremendous reassurance for the safety of the doses proposed for this protocol in that $AUC_{0-24 \text{ hr}}$ exposures as well as the duration of treatment have already far surpassed those being proposed. The highest exposures observed (to date) in the ACC study have been $\sim 45,000 \text{ ng}\cdot\text{hr}/\text{mL}$. These exposures have been well-tolerated and the study will continue to dose escalate until the maximum tolerated dose (MTD) or Phase 2/3 dose has been identified.¹⁰ In addition, the average duration of exposure was 60 days across the 11 dose cohorts. ATR-101 has been extremely well tolerated in a patient population that is markedly less robust (all have advanced stage cancer and most have undergone multiple prior treatment regimens) relative to the CAH patient population.

The dosing rationale is further supported by the 13-week dog toxicity study with $AUC_{0-24 \text{ hr}}$ margins relative to the dog No Observed Adverse Effect Level (NOAEL) of 4.0 to 31.9 for the highest (1000 mg BID) and lowest (125 mg BID) ATR-101 doses planned, respectively.

CAH patients will enter the study with elevated 17-OHP values indicating clinical challenges in obtaining optimal GC replacement therapy. CAH patients can have extremely high 17-OHP levels, $>300 \text{ nmol}/\text{L}$ ($10,000 \text{ ng}/\text{dL}$), relative to reference laboratory normal ranges ($<6 \text{ nmol}/\text{L}$; $<200 \text{ ng}/\text{dL}$)¹⁴. However, complete normalization of 17-OHP is not the therapeutic goal, as this typically results in overtreatment with GC.¹⁴ Acceptably treated CAH patients generally have mildly elevated steroid levels.¹⁴ Thus, the overall goal of the study is to show clinically meaningful decreases in 17-OHP that are aligned with clinical practice goals and to demonstrate similar decreases in the androgen pathway (i.e. androstenedione, testosterone, DHEA, DHEA-S). The study design and dose levels are appropriately supported by existing clinical and nonclinical data.

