3.3 Efficacy Assessment

Efficacy will be assessed by changes in adrenal steroids and steroid intermediates. 17-OHP will serve as the **primary outcome measure** as this adrenal steroid intermediate is used diagnostically and to aid in the management of exogenous GC replacement therapy in clinical practice. However, absolute target values for 17-OHP or androgens do not currently exist in treatment guidelines put forth by any of the medical societies. The entry criteria for 17-OHP is set at ≥ 4 x ULN which is intended to enroll subjects that are not optimally controlled while on exogenous steroid replacement therapy. It is anticipated that most subjects will enter with 17-OHP levels markedly higher than 4 x ULN. The primary efficacy outcome measure will be aligned to the clinical goal of achieving a mildly elevated 17-OHP level which for this study is defined as ≤ 2 x ULN. However, other key efficacy parameters in the androgen pathway (androstenedione, testosterone, DHEA, DHEA-S) will also serve to define efficacy.

The majority of CAH subjects will enter the study on both GC and MC replacement (75% of classic CAH subjects have deficiencies in both pathways). However, plasma renin activity (PRA) and aldosterone will be assessed to determine the potential impact on the MC pathway.

ACTH levels will be assessed to determine potential effects on the hypothalamic-pituitary-adrenal (HPA)-axis. Glucocorticoid replacement doses are expected to remain unchanged so no significant changes in ACTH are anticipated. Confirmation of stable ACTH levels associated with decreases in 17-OHP and androgens will help to establish the ATR-101 pharmacodynamic effects. Increased GC levels, secondary to decreased hepatic metabolism (ATR-101 CYP3A effect; see Section 5.4), could potentially lead to decreased ACTH and subsequently decreased 17-OHP levels. This could potentially confound assessment of direct ATR-101 effects on adrenal steroid and steroid intermediate synthesis. Therefore, assessment of GC levels will also be done during the study.

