## 4 STUDY ENDPOINTS

#### 4.1 Efficacy Assessment

Efficacy will be assessed by changes in adrenal steroids and steroid intermediates.

17-hydroxyprogesterone (17-OHP) will serve as the **primary outcome measure** as this adrenal steroid intermediate is used diagnostically and to aid in the management of exogenous glucocorticoid (GC) replacement therapy in clinical practice. However, absolute target values for 17-OHP or androgens do not currently exist in treatment guidelines put forth by any of the medical societies. The entry criterion for 17-OHP is set at  $\geq 4x$  upper limit of normal (ULN) (ULN adjusted as needed for the menstrual cycle phase of subjects who are premenopausal women), which is intended to enroll subjects who are not optimally controlled while on exogenous steroid replacement therapy. It is anticipated that most subjects will enter with 17-OHP levels markedly higher than  $4xULN$ . The primary efficacy outcome measure will be aligned to the clinical goal of achieving a mildly elevated 17-OHP level, which for this study is defined as  $\leq 2xULN$ . However, given the high baseline 17-OHP levels anticipated, the percentage change in 17-OHP and changes in other key efficacy parameters in the androgen pathway (androstenedione, testosterone, dehydroepiandrosterone [DHEA], dehydroepiandrosterone sulfate [DHEA-S]) will also serve to define efficacy.

The majority of CAH subjects will enter the study on both GC and mineralocorticoid (MC) replacement (75% of classic CAH subjects have deficiencies in both pathways). Direct renin and aldosterone will be assessed to determine the potential impact on the MC pathway.

ACTH levels will be assessed to determine potential effects on the hypothalamic-pituitary-adrenal (HPA)-axis. GC replacement doses are expected to remain unchanged. Confirmation of low GC levels associated with decreases in 17-OHP and androgens with ATR-101 dosing will help to establish the pharmacodynamic effects of ATR-101. Increased GC levels, secondary to decreased hepatic metabolism (ATR-101 CYP3A effect), could potentially lead to decreased ACTH and subsequently decreased 17-OHP levels. This could potentially confound assessment of direct ATR-101 effects on adrenal steroid and steroid intermediate synthesis. Therefore, assessment of GC levels will also be done during the study.

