## **6 STATISTICAL METHODOLOGY**

### **6.1 Sample Size Determination**

Sample size considerations are based on a Simon 2-stage Minimax design with 1-sided alpha of 5% and 80% power.

Stage 1 consists of 9 completed subjects. The study will stop at Stage 1 if either of the following conditions are met:

- Futility criteria: defined as  $\leq 2$  of 9 (22%) subjects having a Day 15 17-OHP  $\leq 2 \times \text{ULN}$  or a negative mean percentage change (i.e., decrease) in 17-OHP from Day 1 to Day 15 for Dose Levels 1-5
- Success criteria: defined as  $\geq 7$  of 9 (78%) subjects having a Day 15 17-OHP  $\leq 2 \times \text{ULN}$  or a negative mean percentage change (i.e., decrease) in 17-OHP from Day 1 to Day 15 for Dose Levels 1-5

Stage 2 will commence if 3, 4, 5, or 6 of the 9 subjects meet the primary outcome measure. In this scenario, accrual will continue with up to 8 additional subjects for a total of no more than 17 subjects. Accrual may stop earlier with sufficient evidence for further development if a total of 7 or more subjects respond (minimum observed response rate of 7/17, 41%).

The study medical monitor along with the Sponsor may determine if a subject will be replaced in order to have a minimum of 9 evaluable subjects for Stage 1. Possible reasons for replacement include extreme noncompliance with study drug not related to an AE, and noncompliance with the protocol such as the use of prohibited medications that could confound results.

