## 6.8 Primary Efficacy Analyses

The percentage of responders will be tabulated for the Safety Population overall. A responder is defined as a subject who meets the primary outcome measure of Day 15 17-OHP  $\leq 2 \times \text{ULN}$  (ULN adjusted as needed for the menstrual cycle phase of subjects who are premenopausal women) at any dose level.

The percentage of subjects showing “drug effect” will be tabulated for the Safety Population overall. A subject showing “drug effect” is defined as a subject who is a responder or who has a negative mean percentage change in 17-OHP from Day 1 to Day 15 for Dose Levels 1-5.

The percentage of responders and percentage of subjects showing “drug effect” will also be tabulated for the Per Protocol Population overall as a sensitivity analysis to test the robustness of the primary result.

The change and percentage change in 17-OHP will also be calculated from Day 15 to Day 1 of the next dose level as follows:

- Change and percentage change from Dose Level 1 Day 15 to *Dose Level 2 Day 1*
- Change and percentage change from Dose Level 2 Day 15 to *Dose Level 3 Day 1*
- Change and percentage change from Dose Level 3 Day 15 to *Dose Level 4 Day 1*
- Change and percentage change from Dose Level 4 Day 15 to *Dose Level 5 Day 1*
- Change and percentage change from Dose Level 5 Day 15 to *Final Study Visit (Visit Day 29)*

The percentage of placebo responders will be tabulated for the Safety Population overall. A placebo responder is defined as a subject who meets Day 1/Final Study Visit 17-OHP  $\leq 2 \times \text{ULN}$  at any dose level, i.e. the 17-OHP at the italicized visit above is  $\leq 2 \times \text{ULN}$ .

The percentage of subjects showing “placebo effect” will be tabulated for the Safety Population overall. A subject showing “placebo effect” is defined as a subject who is a placebo responder or who has a negative mean percentage change in 17-OHP from Day 15 to Day 1 of the next dose level.

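### The 17-OHP drug-effect count keeps only the direction of change; the size of the Day 1 to Day 15 fall gets no interval and no test

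*SAP*

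**What the plan says.** Protocol 3.2 states that "the overall goal of the study is to show clinically meaningful decreases in 17-OHP", in line with clinical practice. Protocol 3.3 sets the outcome at ≤2xULN and acknowledges that "absolute target values for 17-OHP or androgens do not currently exist in treatment guidelines put forth by any of the medical societies". SAP 4.1 adds a second strand: "given the high baseline 17-OHP levels anticipated, the percentage change in 17-OHP" is also to help define efficacy, together with changes in the androgens.

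SAP 6.8 turns these into two efficacy counts. One is the percentage of responders (Day 15 17-OHP ≤2xULN at any dose level). The other is the percentage showing a drug effect, meaning a subject who is "a responder or who has a negative mean percentage change in 17-OHP from Day 1 to Day 15" over Dose Levels 1 to 5. The numerical change that SAP 6.8 itemises runs from Day 15 to the next Day 1, which is the washout direction. SAP 6.9 summarises the Day 1 to Day 15 change for all steroid hormones and intermediates by dose level, but 17-OHP is not among the measures it then names.

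On design, SAP 6.1 says: "Sample size considerations are based on a Simon 2-stage Minimax design with 1-sided alpha of 5% and 80% power". It applies the drug-effect definition to the Stage 1 futility (≤2 of 9) and success (≥7 of 9) limits. It then says that "Stage 2 will commence if 3, 4, 5, or 6 of the 9 subjects meet the primary outcome measure", with 7 responders among at most 17 as the final boundary.

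**The concern.** 17-OHP is a continuous measurement, taken before and after active treatment at up to five dose levels per subject. Reducing the average change to its sign discards the information that the stated goal needs. A non-responder averaging a 1% fall and one averaging a 90% fall are recorded identically.

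The responder count cannot fill the gap, because the fall it demands depends on where the subject starts. From the 4xULN entry floor, reaching 2xULN takes a fall of 1 − 2/4 = 50%. Protocol 3.2 illustrates very high values with 10,000 ng/dL against a normal limit of 200 ng/dL, which is 50xULN; from there the required fall is 1 − 2/50 = 96%. A subject who falls 90% from 50xULN ends at 5xULN and is a non-responder.

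A sizeable fall that stops short of target would therefore appear as few responders plus a count of minus signs, with no estimate of precision. Conversely, a majority of small, noisy falls could be read as evidence of activity.

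**Working it through.** **1. Reproduce the design.** The inputs from SAP 6.1 are 9 then 17 subjects, Stage 2 if 3 to 6 of 9, success at 7, and "1-sided alpha of 5% and 80% power". The null and target response rates are not stated. A minimax search returns these boundaries for p0 = 0.20 and p1 = 0.50, so that pair is inferred. With

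P(pass | p) = Σ(x = 3 to 6) P(X9 = x)·P(X8 ≥ 7 − x) + P(X9 ≥ 7),

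P(pass | 0.20) = 0.034 and P(pass | 0.50) = 0.806. The stated alpha limit and power are met. The early success stop changes nothing, since 7 already meets the final boundary.

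**2. Sign count against a paired t-test, nine subjects.** Let d be the mean fall divided by the between-subject SD of the per-subject mean changes. It is an assumption, since no SD or expected fall is given. With no effect and symmetric changes, P(≥7 of 9) = 46/512 = 9.0% and P(≥8 of 9) = 10/512 = 2.0%. With an effect, P(negative) = Φ(d) = 0.758, 0.788 and 0.841 for d = 0.7, 0.8 and 1.0. T-test power is from the noncentral t with 8 degrees of freedom.

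| d | ≥8 of 9 (2.0%) | t-test at 2.0% | gain, points | ≥7 of 9 (9.0%) | t-test at 9.0% | gain, points |
|---|---|---|---|---|---|---|
| 0.7 | 32.0% | 40.5% | 8.5 | 62.3% | 73.8% | 11.4 |
| 0.8 | 40.1% | 50.6% | 10.5 | 70.6% | 82.0% | 11.4 |
| 1.0 | 57.0% | 70.1% | 13.1 | 84.0% | 93.0% | 9.0 |

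At equal alpha, the cost of using only the sign is about 8 to 13 points.

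**3. Two-stage boundaries applied to the sign count, no drug effect.** With one dose level, a negative change has probability 0.50, which is the inferred target rate, so the rule passes 80.6% of the time. Averaging percentage changes over several levels lowers that probability, because percentage changes are skewed upwards. With five independent levels and a log-ratio SD of 0.2, 0.4, 0.6 or 0.8 (assumed), P(negative) is 0.43, 0.37, 0.32 or 0.27 and the rule passes 61.5, 40.9, 24.9 or 14.4% of the time.

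The whole design was also simulated, with 20,000 trials per setting, five levels and stopping at the first Day 15 value ≤2xULN. Assumed: median baseline 8 to 30xULN with log-SD 0.7, and visit noise log-SD 0.35 to 0.7. With no effect, the rule on the drug-effect count passes about 10 to 34% of the time. This agrees with the five-level figures, since the log-ratio SD is then 0.35√2 = 0.49 to 0.7√2 = 0.99. If the top dose halves 17-OHP, it passes about 81 to 100%.

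**4. The responder cut answers a different question.** Assume a 50% fall, log-SD 0.6, one assessment and 17 subjects. From 10xULN, P(response) = Φ(−ln 2.5/0.6) = 0.063 and P(≥7 of 17) is below 0.001. From 4xULN, P(response) = 0.50 and P(≥7 of 17) = 0.83. A t-test on the log change has power 0.998 in both cases.

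**The case against.** Four points deserve weight.

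First, a reader might infer that the plan only counts subjects and discards the size of the change. The documents do not support that. SAP 6.9 covers all steroid intermediates, 17-OHP is one by the plan's own description, and the list that omits it may be illustrative, since it also omits total testosterone. What is missing is an interval or test, and a clear statement that 17-OHP is covered.

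Second, a reader might infer a power loss of about 30 points by setting the 8-of-9 count (40% at d = 0.8) against a t-test at 5% (71%). That compares a 2.0% test with a 5% test. Moreover, SAP 6.1 uses 7 of 9, where power is close to that of a 5% t-test (71% for both at d = 0.8), although that count runs at 9.0%. If the two-stage boundaries apply to the count, low power is not the fault at all; error control is.

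Third, a reader might infer that ≤2xULN is the wrong endpoint. It is the prespecified clinical goal, and the design has about 80% power for the inferred 50% response rate. Its low power for a smaller fall reflects a different question.

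Fourth, the Protocol synopsis calls the analyses qualitative, and this is a proof-of-concept study of 9 to 17 subjects. Descriptive reporting is a legitimate choice, and preferring a t-test is partly taste. This stands in part. But the design claims a one-sided 5% alpha, and an interval is a description too.

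**Conclusion.** The point holds in limited form. The drug-effect count cannot say whether a fall in 17-OHP is clinically meaningful, and no section gives the Day 1 to Day 15 change an interval or test. That conclusion needs no assumptions.

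The sizes do need them. The loss of about 8 to 13 points rests on nine subjects, d of 0.7 to 1.0 and roughly normal changes. The 10 to 34% pass rate rests on the simulated baselines and noise, and on reading the Stage 2 and final boundaries as applying to the drug-effect count. SAP 6.1 does not settle that. Its Stage 1 limits use the new definition, while its Stage 2 sentence still refers to the primary outcome measure. A reader should therefore not conclude that the trial's 5% error rate is certainly lost, only that it would be under that reading. If Stage 2 rests on ≤2xULN alone, the inferred 3.4% from step 1 describes the responder rule, not the drug-effect count.

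**What to change.** - Keep the ≤2xULN responder percentage as the primary endpoint in SAP 6.8, and label the drug-effect sign count as descriptive only.
- Name 17-OHP in SAP 6.9. Report the geometric mean Day 15/Day 1 ratio with a two-sided 90% CI at each dose level and overall.
- Take these from a mixed model on log 17-OHP at Day 1 and Day 15, with fixed effects for visit (Day 15 on active versus Day 1 after placebo), dose level and their interaction, and a random subject effect. The visit term is essential, because without it the model does not identify a drug effect. The by-level ratios matter because Protocol 3.2 intends Dose Level 1 to be non-effective, so an overall average is diluted.
- Exclude Final Study Visit samples taken after the morning replacement steroid, which Protocol 7.6 allows, or use them only in a sensitivity analysis.
- Use a one-sample t-test on each subject's mean log ratio as a simple check.
- Judge clinical meaning from the estimate and its interval. An upper bound below 1 is by itself another cut at zero.

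The cost is SAP wording and one or two tables, with no extra samples, visits or subjects. There are two limits. The ratio shows a fall, not attainment of target, so the responder percentage must stay beside it. And because responders stop early, the simple t-test's error rate can slightly exceed 5% (about 5 to 7% in simulation).

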- ^c For each Dose Level there will be 14 days of treatment with ATR-101 and 14 days of treatment with placebo. For each portion there should be a minimum of 11 days of treatment and a maximum of +3 days is allowed beyond the scheduled 14 days.
- ^d Dose assessment will be performed prior to dosing on Day 1 of Dose Levels 2, 3, 4 and 5 as needed. The PI or SI will review the 17-OHP results obtained on Day 15 and determine whether the Final Study Visit will be conducted (17-OHP \leq 2 x ULN on Day 15) or whether the next Dose Level, Day 1 Visit will be conducted (17-OHP > 2 x ULN on Day 15).
- ^e 17-OHP results from Screening and Baseline Lead-In Period will be used in this evaluation of inclusion criteria.
- ^f Complete physical examinations will be performed at Screening and the Final Study Visit or Early Termination Visit. An abbreviated (brief) physical exam will be performed at Day 1 of Baseline Lead-In Period, pre-dose on Day 1 and Day 15 of each dose level.
- ^g Vital signs (blood pressure, pulse, respiration rate, and temperature) and body weight will be measured at Screening, Day 1 of the Baseline Lead-In Period, pre-dose and 1, 2, and 4 hour post-dose on Day 1 of each dose level, Day 15 for each dose level, and at the Final Study Visit or Early Termination Visit. Height will be measured at Screening.
- ^h All subjects will have 12-lead ECG assessments at Screening, Day 1 pre-dose and 2 hours post-dose for each dose level, Day 15 pre-dose for each dose level, and at the completion of the Placebo Washout Period on Day 29.
- ⁱ Blood samples for steroid hormones and steroid intermediates including 17-OHP, androstenedione, cortisol, testosterone, ACTH, free testosterone, SHBG, aldosterone, 11-DOC, PRA, DHEA and DHEAS will be obtained at Screening, Day 1 of Baseline Lead-In Period, pre-dose on Day 1 and Day 15 of each dose level and at the Final Study Visit or Early Termination Visit. All samples will be collected prior to 10 AM.
- ^j Blood samples for exogenous glucocorticoid levels (Betamethasone, Budesonide, Dexamethasone, Fludrocortisone, Flunisolide, Fluorometholone, Hydrocortisone, Megestrol acetate, Methylprednisolone, Prednisolone, Prednisone, Triamcinolone, Triamcinolone acetonide) will be obtained as appropriate for each subject.

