3.1.2 Baseline Lead-in Period

Eligible subjects will enter a placebo Baseline Lead-in Period. This 14 day period allows subjects to get accustomed to being in a clinical trial (e.g. avoiding prohibited medications) and taking investigational medicinal product (IMP) on a regular basis. This period also provides an opportunity to develop a more accurate assessment of adrenal steroids and steroid intermediates and documentation of exogenous steroid replacement therapy (GC and MC).

In order to obtain unbiased information, the subjects will not know that the tablets received are placebo and do not contain active drug substance (ATR-101). Placebo tablets for this period will look identical to ATR-101 125 mg tablets (i.e. Dose Level 1). However, the study center personnel will be aware that the tablets are placebo.

At the conclusion of the Baseline Lead-in Period, subjects will be assessed for protocol compliance, including IMP compliance (tablet counts) and whether it is appropriate to proceed in the study.

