**Figure 1. ATR-101-201 Study Design**

Each subject will complete a Screening Period of up to 21 days to assess inclusion and exclusion criteria. Baseline status will be established with a 14-day single-blind, placebo Lead-in Period. Exogenous GC and MC replacement therapy must be maintained throughout the duration of the study. Each dose level, comprised of ATR-101 administered for 14 days followed by a 14-day placebo washout, will last for a total of 28 days (see Figure 2 below). All subjects will start at Dose Level 1, ATR-101 125 mg twice daily (BID), for 14 days. Efficacy and safety will be assessed after the 14-day ATR-101 treatment period (on the morning of Day 15). Immediately after the completion of the ATR-101 treatment period, a 14-day single-blind, placebo Washout Period (placebo matching ATR-101 125 mg) will take place. The efficacy assessment obtained on Day 15 will be reviewed by the Principal Investigator (PI) or Sub-investigator (SI) to determine whether the subject has met the

primary outcome measure or whether the subject should continue to the next dose level (if there are no safety issues).

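### SAP 6.8 measures 'placebo effect' only in washouts that follow ATR-101 and leaves out the placebo lead-in, so the figure shows drug offset and not how often 17-OHP falls on placebo

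*SAP*

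**What the plan says.** The trial has no parallel control. SAP 6.8 tabulates four percentages for the Safety Population: responders, subjects with drug effect, placebo responders and subjects with placebo effect.

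- **Drug effect:** the subject is a responder or "has a negative mean percentage change in 17-OHP from Day 1 to Day 15 for Dose Levels 1-5".
- **Placebo effect:** the subject is a placebo responder or "has a negative mean percentage change in 17-OHP from Day 15 to Day 1 of the next dose level".
- **Placebo intervals:** these are introduced by "The change and percentage change in 17-OHP will also be calculated from Day 15 to Day 1 of the next dose level as follows". The five entries run from Day 15 of Dose Levels 1–4 to the next level's Day 1, and from Dose Level 5 Day 15 to the Final Study Visit.
- **Placebo responder:** "A placebo responder is defined as a subject who meets Day 1/Final Study Visit 17-OHP" at or below 2×ULN, limited to the listed end visits by the clause "i.e. the 17-OHP at the italicized visit above is" within the threshold.

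Dose Level 1 Day 1, the end of the lead-in, is not a listed end visit. SAP 6.9 covers only Day 1 to Day 15 and Day 15 to the next Day 1, so it does not analyse the lead-in change either.

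On the lead-in itself, SAP 5.1 says "Baseline status will be established with a 14-day single-blind, placebo Lead-in Period", and Protocol 3.1.2 adds "This period also provides an opportunity to develop a more accurate assessment of adrenal steroids and steroid intermediates". Under footnote i of the protocol's Schedule of Assessments, steroid samples "will be obtained at Screening, Day 1 of Baseline Lead-In Period, pre-dose on Day 1 and Day 15 of each dose level". Both ends of the lead-in are therefore measured.

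**The concern.** A row headed placebo effect beside one headed drug effect invites the reader to take it as the rate at which 17-OHP falls on placebo. Here it cannot be that. Protocol 3.2 expects each subject to be back at baseline status after washout. If the drug has worked, 17-OHP should therefore rise over the washout, and a rise is scored as no placebo effect. The better the drug works, the rarer placebo effect becomes, even if placebo does nothing.

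The question a reader will have is how often 17-OHP falls over two weeks in this trial without ATR-101, for example through steadier use of replacement steroids. The lead-in is the one placebo interval whose expected change does not depend on ATR-101, and no planned analysis reports that change. A subject already at or below 2×ULN after placebo alone would not be counted as a placebo responder on that visit.

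**Working it through.** The plan gives no target or expected value for the placebo rows, so there is no stated figure to reproduce. The check is how the tabulated rates behave under the SAP's own definitions.

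**Inputs from the documents.** The intervals and definitions are those of SAP 6.8. Entry requires 17-OHP ≥4×ULN at Screening and at the Baseline Lead-in (Protocol 4.2). Escalation stops once Day 15 17-OHP is ≤2×ULN (Protocol 3.1).

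**Assumptions, because the documents give none.**
- Independent log-normal visit noise with within-subject log SD σ of 0.3–0.5; 0.2 was also tried.
- Median 17-OHP of 10 or 30×ULN, with 6×ULN also tried; between-subject log SD 0.6.
- The same true fall f at every dose level, with full return in washout.
- 200,000 simulated subjects per setting.

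**Step 1: one noise-free interval.** A fall f followed by full return is a washout change of 1/(1−f) − 1. For f = 10%, 20%, 30% and 50% this is +11%, +25%, +43% and +100%.

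**Step 2: one interval with noise.** The chance of a fall on drug is Φ(−ln(1−f)/(σ√2)), and the chance of a fall in the following washout is one minus that. At σ = 0.3, σ√2 = 0.424:

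| True fall f | −ln(1−f) | Fall on drug | Fall in washout | Fall on placebo with no prior drug |
|---|---|---|---|---|
| 0% | 0 | 50% | 50% | 50% |
| 10% | 0.105 | 60% | 40% | 50% |
| 20% | 0.223 | 70% | 30% | 50% |
| 30% | 0.357 | 80% | 20% | 50% |

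The last column ignores selection at entry.

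**Step 3: the SAP definitions.** The SAP averages raw percentage changes over up to five intervals. The ratio of two independent log-normal values has mean exp(σ²), so with no drug effect the expected change is exp(0.09) − 1 = +9.4% at σ = 0.3. The multi-interval mean is therefore negative less than half the time. Simulated at σ = 0.3, median 10×ULN:

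| True fall | SAP drug effect | SAP placebo effect | Lead-in fall (single interval) |
|---|---|---|---|
| 0% | 36% | 36% | 51–52% |
| 10% | 57% | 19% | 51–52% |
| 20% | 78% | 7% | 51–52% |
| 30% | 93% | 2% | 51–52% |

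Over σ = 0.3–0.5 an inactive drug gives 29–36% in both SAP columns (about 40% at σ = 0.2). The lead-in figure is 50–53% at medians of 10 and 30×ULN, reaching about 56% over all settings tried. It exceeds 50% because its first sample is selected at ≥4×ULN. It does not move with f, whereas the SAP placebo rate does.

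**Step 4: what must not be compared.** The lead-in column is a single interval and the SAP drug-effect column is a mean of up to five. With an inactive drug they read about 50–56% and 29–36%, a gap created by the averaging. The like-for-like partner is a single Day 1 to Day 15 change, as in Step 2.

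**The case against.** The best defence is that the washout contrast is the intended evidence. Protocol 3.2 gives the washout the task of verifying that steroid changes are due to ATR-101, and a rise on withdrawal does support that. The lead-in's stated purposes are acclimatisation and baseline. This stands: the washout change should be kept, and the fault lies in its label and in the missing lead-in row.

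Four stronger readings are tempting, and the documents do not support them.

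- **That the definition manufactures efficacy.** Each Day 15 value ends a drug interval and starts a placebo interval, so a chance low value counts as a fall on drug and a rise on placebo. But a chance low Day 1 value does the reverse. The SAP tabulates separate overall percentages, and with an inactive drug these are equal. Any link between the two measures within a subject is not tabulated.
- **That the trial's error rates suffer.** Placebo effect enters no test and is not in the stopping criteria of SAP 6.1 or 7.
- **That the lead-in is the only period off drug.** Washouts contain no ATR-101 dosing either. The lead-in is the only placebo period that ATR-101 does not precede.
- **That the lead-in rate should replace placebo effect as the comparator for drug effect.** Step 4 shows this would be biased the other way. At σ = 0.5 and a true 10% fall, drug effect is about 41–44% against 50–56% for the lead-in, so a working drug would look worse than placebo.

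Dose Level 1 Day 1 steroid values are also not wholly ignored: SAP 6.5 summarises them as baseline, with minimum and maximum. What is missing is the lead-in change and the count at or below 2×ULN.

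**Conclusion.** The point holds as a matter of labelling and omission. SAP 6.8's placebo measures come only from visits after ATR-101, and the placebo-effect rate falls as the drug works: at σ = 0.3, from about 36% with no effect to 19%, 7% and 2% at true falls of 10%, 20% and 30%. It measures offset of the drug effect and does not estimate how often 17-OHP falls on placebo.

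The direction follows from the definitions together with the protocol's own expectation of return to baseline. The percentages depend on assumed variability, entry level, a constant fall across dose levels and full return in washout. A real drug effect is needed for the gap to open; an inactive drug gives equal rates. Alpha, power and the Stage 1 decision are untouched by the placebo rows. This is a minor, cheap improvement to a descriptive table.

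**What to change.** In SAP 6.8:

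1. Report on a separate line, for the Safety Population, the number and percentage with 17-OHP ≤2×ULN at Dose Level 1 Day 1 pre-dose, the end of the lead-in.
2. Add a placebo lead-in row giving change, percentage change and proportion falling in 17-OHP from Lead-In Day 1 to Dose Level 1 Day 1. State that it is to be read only beside single-interval Day 1 to Day 15 changes within each dose level, and not against the multi-level drug-effect percentage.
3. Keep the Day 15 to next Day 1 change, and call it reversal after withdrawal in place of placebo effect.

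The cost is SAP wording, one count and one table row. Both samples are already scheduled, and no planned analysis is lost. The downside is that Lead-In Day 1 is selected at ≥4×ULN, so regression to the mean lifts the lead-in fall rate slightly (about 50–56% in place of 50% under the assumptions tried), and it is a single interval in at most 17 subjects under the planned design. A footnote should say so. The count in item 1 uses a value that is not itself an entry criterion, so it avoids the direct selection that affects Lead-In Day 1.
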